
## A ClinSync

Protocol for Drug-Drug Interaction Study of Spironolactone and Digoxin (Fasting Condition) Confidential

#### Day 07

Name O	f Cooked Food	Wt. In (g)	Proteins (g)	Carbohydrates (g)	Fats (g)	K.Cal
Breakfast	Idly (4)	160	6.5	45.5	0.4	211.6
0.50 hour	Sambar	100	2.5	7	2.5	60.50
after dosing	Chutney (Coconut)	80	3.0	9.0	15	179.00
					Tota	1 = 451.10
	Plain Rice	500	11	125	0.75	550.75
Lunch	Pulka(1)	35	03	17.5	0.455	86.05
04.00 hours	Red Gram Dhai	100	4.4	12.5	1.4	80.20
after dosing	Tomato Methi Curry	100	5.00	10.0	5.00	68.00
	Chutney	30	0.3	1.3	1.6	20.80
	Sambar	100	2.5	7	2.5	60.50
	Curd	100	3.1	3.0	4.0	60.40
	Papad (1)	10	1.2	0.8	1.5	21.50
Snacks 08.00 hours					Total	= 948.20
after dosing	Masala Vada (Gare)	60	6.5	20.0	7.0	169.00
atter dosting					Total	= 169.00
	Plain Rice	500	11	125	0.75	550.75
	Pulka(1)	35	03	17.5	0.45	86.05
Dinner	Red Gram Dhal	100	4.4	12.5	1.4	80.20
12.00 hours	Egg Curry	100	6.0	7.0	7.0	115.00
after dosing	Chutney	30	0.3	1.3	1.6	20.80
unter dooming	Sambar	100	2.5	7	2.5	60.50
	Curd	100	3.1	3.0	4.0	60.40
	Papad (1)	10	1.2	0.8	1.5	21.50
					Total	= 995.20
				Grand	l Total =	2563.50

[figure not shown]
## 🔬 ClinSync

Protocol for Drug-Drug Interaction Study of Spironolactone and Digoxin (Fasting Condition) Confidential

#### Day 08

Name O	of Cooked Food	Wt. In (g)	Proteins (g)	Carbohydrates (g)	Fats (g)	K.Cal
Breakfast	Vada (4)	88	10.5	30	11.5	265.50
0.50 hour	Sambar	75	1.75	4.75	2.00	44.00
after dosing	Chutney (Coconut)	80	3.00	9.00	15.0	179.00
			***	ές της πολογητικής του	Tota	1 = 488.50
	Plain Rice	500	11	125	0.75	550.75
Lunch	Pulka(1)	35	03	17.5	0.455	86.05
04.00 hours	Red Gram Dhal	100	4.4	12.5	1.4	80.20
after dosing	Beans curry	100	4.0	08	5.0	93.00
	Chutney	30	0.3	1.3	1.6	20.80
	Sambar	100	2.5	7	2.5	60.50
	Curd	100	3.1	3.0	4.0	60.40
	Papad(1)	10	1.2	0.8	1.5	21.50
Snacks 08.00 hours					Total	= 973.20
after dosing	Punagulu	60	4.5	16.0	8.0	154.00
atter dosnig	Tomato Chutney	60	0.6	2.6	3.2	41.60
					Total	= 195.60
	Plain Rice	500	11	125	0.75	550.75
Dinner	Pulka(1)	35	03	17.5	0.45	86.05
12.00 hours	Red Gram Dhal	100	4.4	12.5	1.4	80.20
after dosing	Capsicum Curry	100	1.00	12.00	6.00	106.00
	Chutney	30	0.3	1.3	1.6	20.80
	Tomato Rasam	100	1.0	4.0	2.0	38.00
	Curd	100	3.1	3.0	4.0	60.40
	Papad (1)	10	1.2	0.8	1.5	21.50
I					Total	= 963.70
مىرىدىنى				Grand	Total =	2621.00

Protocol for Drug-Drug Interaction Study of Spironolactone and Digoxin (Fasting Condition) Confidential

Day 09

Name	Of Cooked Food	Wt. In (g)	Proteins (g)	Carbohydrates (g)	Fats (g)	K.Cal
Breakfast	Chapathi	75	6.5	37.0	3.5	205.50
0.50 hour	Potato Curry	100	1.5	16	6.0	124.00
after dosing						1
					Tota	1 = 329.50
	Plain Rice	500	11	125	0.75	550.75
Lunch	Pulka(1)	35	03	17.5	0.45	86.05
04.00 hours	Red Gram Dhal	100	4.4	12.5	1.4	80.20
after dosing	Carrot Peas curry	100	3.0	10.0	6.0	106.00
	Chutney	30	0.3	1.3	1.6	20.80
	Sambar	100	2.5	7	2.5	60.50
	Curd	100	3.1	3.0	4.0	60.40
	Papad (1)	10	1.2	0.8	1.5	21.50
Snacks		1				= 986.20
08.00 hours	Samosa(1)	65	2.5	21.0	12.5	206.50
after dosing					Total	= 206.50
	Veg pulavo	600	14	114	15	647.00
Dinner 12.00 hours	Mirch ka Salan(Capsicum)	190	3	18	15.4	222.60
after dosing	Sambar	100	2.5	7	2.2	60.50
	Curd	100	3.1	3.0	4.0	60.40
			and a state of the	Grand		= 990.50 2512.70

Note: 1g PROTIEN = 4 K.Cal; 1g CHO = 4 K.Cal; 1g FAT = 9 K.Cal

**References:** Nutritive Value of Indian Foods by Gopalan et.al, NIN, Count What You Eat by Swaran Pasricha, NIN and Food Composition Table of Indian foods 2017, NIN.

Protocol for Drug-Drug Interaction Study of Spironolactone and Digoxin (Fasting Condition) Confidential

PARAMETER	LABORATORY REFERENCE RANGES
	HEMATOLOGY
Homoolahin	Male:13-18 g/dL
Hemoglobin	Female:11.5-16 g/dL
WBC Count	4000 – 11000 Cell/cumm
RBC Count	4.5- 5.5 mil/μl
Platelet Count	1.50-4.50 lakhs/cumm
Neutrophils	40-75 %
Lymphocytes	20-40 %
Eosinophils	01-06 %
Monocytes	02-10 %
Basophils	00-01 %
ESR	0-15 mm/hr
CLIN	CAL BIOCHEMISTRY
Bilirubin Total	<1.0 mg/dL
Bilirubin Direct	<0.3 mg/dL
Alkaline Phosphatase	50-136 U/L
AST/SGOT	15-37 U/L
ALT/SGPT	30-65 U/L
Protein Total	6.4-8.2 g/dL
Albumin	3.4-5.0 g/dL
Urea	10-50 mg/dL

#### Appendix-IV: Laboratory Reference Ranges

0.: C-CMP-SPI-001; Version 02; Date: 07 Aug 2018

VASA ETH

VASAVEINSTITUTIONAL ETHIC: COMMITTEE ED ∞, € ; 80 1997 - 19

٠

.

# ----------

[figure not shown]

6.4 Sampling Procedure	stored upright in a box containing dry ice or in a freezer at a temperature of $-20 \pm 5^{\circ}$ C for interim storage (pre-dose and post- dose samples up to 4.00 hours) and then will be transferred to $-70 \pm$ $15^{\circ}$ C at the clinical site.	freezer of CCM department at -70 ± 10°C.	Change in storage temperature due to revision of the SOP

Note: The above said changes are applicable throughout the protocol and related documents.

(Sign & date) Prepared By (MW): [name] 19 Dec 2-018 Reviewed By (QA): (Sign & date) Approved By (PI/CI): (Sign & date) VASAVI INSTITUTIONAL

25007A-01

Page 6 of 7

ClinSync

## **16.1.2 SAMPLE CASE REPORT FORM**

Statistical Analysis Plan: February 2018

An open label, balanced, randomized, single-dose, two-treatment, two-sequence, twoperiod, crossover oral drug-drug interaction study of spironolactone (perpetrator) and Digoxin (substrate drug) in healthy adult human subjects under fasting condition.

PHARMACOKINETIC ASSESSMENTS:

Concentration data of subjects versus time, which are received after analysis of samples, will be included in the final data analysis. Data from subjects with missing concentration values (missed blood samples, lost samples, samples unable to be quantified) may be used if pharmacokinetic parameters can be estimated using remaining data points, otherwise data from these subjects will be excluded from the final analysis.

All concentration values below the limit of quantification (BLQ) will be set to zero for all pharmacokinetic and statistical calculations. Any missing samples will be reported as 'Missing' and will be denoted as "M" while running pharmacokinetic and statistical analysis.

The following pharmacokinetic parameters will be computed using noncompartmental model of Phoenix WinNonlin Professional Software Version 6.4 (Pharsight Corporation, USA) or above.

Pharmacokinetic Parameters for digoxin in plasma:

Primary Pharmacokinetic parameters

Cmax : Maximum measured plasma concentration.

AUC0-96 : Area under the plasma concentration versus time curve from time 0 to the 96 hour time point concentration, calculated by linear trapezoidal method.

Secondary Pharmacokinetic parameters

Tmax : Time to achieve maximum plasma concentration. If the maximum value occurs at more than one time point, Tmax is defined as the first time point with this value.

Pharmacokinetic Parameters for digoxin in urine:

CLR: Renal clearance Ae0-240h/AUC0-240 h

fe: Unchanged drug excreted in urine

For all the above computations, actual time points of the sample collection will be used in case of sample collection deviations.

In clinical phase or sample analysis process, if 3 or more consecutive post dose samples for any subject are found to be missing, samples of such subjects will be analyzed but pharmacokinetic data of those subjects will be excluded from the final statistical analysis.

Pharmacokinetic data of those subjects will be tabulated and reported in the study report as a separate table. However, the data of such subjects will also be considered for statistical analysis if the 3 consecutive post dose samples are the last three samples of elimination phase.

If the pre-dose concentration appears to be > 5% of the Cmax in any subject at any period, the data of such a subject will be excluded from the statistical analysis.

STATISTICAL ANALYSIS

Statistical analysis will be performed by using SAS statistical software version 9.3 or above.

Descriptive statistics of all the pharmacokinetic parameters will be computed and reported for digoxin.

The log-transformed pharmacokinetic parameters Cmax and AUC0-96 were analysed using Type III sum of squares, with the main effects of formulation, period, sequence and subjects nested within sequence as random effect.

Statistical analysis was performed using SAS® package (SAS Institute Inc., USA, Version 9.3).

The presence or absence of DDI between the two treatments (A and B) was concluded based on the statistical results of 90% confidence interval for the ratio of the geometric least squares mean for log-transformed pharmacokinetic parameters Cmax and AUC0-96 for Digoxin. Absence of drug-drug interaction would be established if the 90% CI for the ratio of population geometric means of log-transformed data of Cmax and AUC0-96 between two treatments (A and B), were in the equivalence limits of 80.00 - 125.00% for Digoxin.

Renal clearance (CLR)/ Percent Recovered and unchanged drug excreted in urine (fe)/Amount Recovered for Digoxin in the presence and absence of spironolactone was provided as supportive data.

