# 9.2 DISCUSSION OF STUDY DESIGN, INCLUDING THE CHOICE OF CONTROL GROUPS

This study was designed as an open label, balanced, randomized, single-dose, two-treatment, two-sequence, two-period, crossover, drug-drug interaction study.

The washout period has been chosen based on the elimination half-life of digoxin, such that at least 5-7 half-lives have elapsed after drug administration. The blood collection time points were chosen to accurately characterize the absorption and elimination phases of the plasma concentration versus time curve obtained after dosing.

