### **Pharmacokinetics**

Typical pharmacokinetic endpoints for DDI studies include changes in drug exposure parameters such as  $C_{max}$  and  $AUC_{0.72}$ . Pharmacokinetic sampling times should be sufficient to characterize the  $C_{max}$  and  $AUC_{0.72}$ . The sampling times for single-dose studies should be planned so that the mean difference between the  $C_{max}$  and  $AUC_{0.72}$  is less than 20 percent. Pharmacokinetic results of DDI study will be reported as the geometric mean ratio of the observed pharmacokinetic exposure measures with and without the perpetrator drug and include the associated 90 percent confidence interval. Observed variability of the interaction will also be reported.

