### Elimination

### .} ClinSync

Protocol for Drug-Drug Interaction Study of Spironolactone and Digoxin (Fasting Condition) Confidential

Elimination of digoxin follows first-order kinetics (that is, the quantity of digoxin eliminated at any time is proportional to the total body content). Following intravenous administration to healthy volunteers, 50% to 70% of a digoxin dose is excreted unchanged in the urine. Renal excretion of digoxin is proportional to glomerular filtration rate and is largely independent of urine flow. In healthy volunteers with normal renal function, digoxin has a half-life of 1.5 to 2.0 days. The half-life in anuric patients is prolonged to 3.5 to 5 days.

Pharmacokinetic Parameters:

Parameters	Digoxin
T max (hours)	1 - 3
Mean terminal T 1/2 (days)	1.5 - 2.0

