### 2.2.4 Drug Interactions

Potassium-depleting diuretics are a major contributing factor to digitalis toxicity. Calcium, particularly if administered rapidly by the intravenous route, may produce serious arrhythmias in digitalized patients. Quinidine, verapamil, amiodarone, propafenone, indomethacin, itraconazole, alprazolam, and spironolactone raise the serum digoxin concentration due to a reduction in clearance and/or in volume of distribution of the drug, with the implication that digitalis intoxication may result. Erythromycin and clarithromycin (and possibly other macrolide antibiotics) and tetracycline may increase digoxin absorption in patients who inactivate digoxin by bacterial metabolism in the lower intestine, so that digitalis intoxication may result. Propantheline and diphenoxylate, by decreasing gut motility, may increase digoxin absorption. Antacids, kaolin-pectin, sulfasalazine, neomycin, cholestyramine, certain anticancer drugs, and metoclopramide may interfere with intestinal digoxin absorption, resulting in unexpectedly low serum concentrations. Rifampin may decrease serum digoxin concentration, especially in patients with renal dysfunction, by increasing the nonrenal clearance of digoxin. There have been inconsistent reports regarding the effects of other drugs (e.g., quinine, penicillamine) on serum digoxin concentration. Thyroid administration to a digitalized, hypothyroid patient may increase the dose requirement of digoxin. Concomitant use of digoxin and VASAVI INSTITUTIONAL ETHICS COMMISSION And Antimetics increases the risk of cardiac arrhythmias. Succinylcholine may

Protocol for Drug-Drug Interaction Study of Spironolactone and Digoxin (Fasting Condition) Confidential

cause a sudden extrusion of potassium from muscle cells, and may thereby cause arrhythmias in digitalized patients. Although calcium channel blockers and digoxin may be useful in combination to control atrial fibrillation, their additive effects on AV node conduction can result in advanced or complete heart block. Both digitalis glycosides and beta-blockers slow atrioventricular conduction and decrease heart rate. Concomitant use can increase the risk of bradycardia. Digoxin concentrations are increased by about 15% when digoxin and carvedilol are administered concomitantly. Therefore, increased monitoring of digoxin is recommended when initiating, adjusting, or discontinuing carvedilol.

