### 6.3 Sampling Schedule

Urine & Blood samples collection will be started after the completion of dosing on Day 6.

A total of 11 urine samples will be collected from each subject in each study period.

Urine samples will be collected at intervals of (0.00-1.00), (1.00-2.00), (2.00-4.00), (4.00-6.00), (6.00-8.00), (8.00-12.00), (12.00-16.00), (16.00-24.00), (24.00-48.00), (48.00-72.00) and (72.00-96.00) hours post dose.

Immediately out of the total volume of urine collected at each collection time interval, approximately 10 mL (2 x 5 mL aliquots) of urine samples will be transferred into two pre-labeled containers for analysis. They will be stored at deep freezer maintained at  $-20^{\circ}$ C or lower until dispatched from Clinical Unit to Bioanalytical Department for analysis.

A total of  $25(1 \times 5 \text{ mL})$  blood samples will be collected from each subject in each study period. Blood samples will be collected at pre-dose (0.00) and post dose at 0.25, 0.50, 0.75, 1.00, 1.33, 1.67, 2.00, 2.33, 2.67, 3.00, 3.50, 4.00, 5.00, 6.00, 8.00, 10.00, 12.00, 16.00, 24.00, 36.00, 48.00, 60.00, 72.00 and 96.00 hours post dose in each period.

Note: Blood samples up to 3 hours post dose will be collected at bed side.

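### With AUC0-96 as the only plasma AUC, a digoxin rise caused by reduced clearance would be understated; half-life and AUC0-inf should be reported beside it

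*SAP*

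**What the plan says.** - **Parameters.** The SAP (Pharmacokinetic Assessments) and Protocol Section 9 list Cmax, AUC0-96 and Tmax for plasma. The AUC is "Area under the plasma concentration versus time curve from time 0 to the 96 hour time point concentration, calculated by linear trapezoidal method". Tables 10 and 11 of the study report follow this list. No terminal slope, half-life, AUC0-inf or extrapolated share is planned or reported.
- **Sampling.** Protocol Section 6.3 ends blood sampling with "60.00, 72.00 and 96.00 hours post dose in each period", after samples at 24, 36 and 48 h. Urine is also collected to 96 h.
- **Half-life.** Protocol Section 2.2.3, Elimination: "In healthy volunteers with normal renal function, digoxin has a half-life of 1.5 to 2.0 days".
- **Mechanism.** Protocol Section 2.2.4 lists spironolactone among the drugs that "raise the serum digoxin concentration due to a reduction in clearance and/or in volume of distribution of the drug". Section 2.1.4 says the extent of any true increase is unknown.
- **Rationale.** Study report Section 9.2: "The blood collection time points were chosen to accurately characterize the absorption and elimination phases of the plasma concentration versus time curve".
- **Decision rule.** Protocol Section 10.7 and the SAP declare no interaction only if the 90% CI lies within 80.00-125.00% for both Cmax and AUC0-96.

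**The concern.** At 2.0 to 2.7 half-lives, a sizeable part of the curve lies beyond the last sample. If spironolactone lowers clearance without changing volume, the half-life lengthens under Treatment B. A larger share of the B curve than of the A curve is then cut off, which pulls the AUC0-96 ratio toward 1.

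The trial is about magnitude. Its primary objective is to characterise the profile with and without spironolactone. Section 3.2 asks whether digoxin levels rise, and Section 10.1 justifies 28 subjects by a reliable estimate of the size of the interaction. Section 11.2 calls digoxin a narrow therapeutic index drug. Sampling is said to cover the elimination phase, yet no elimination parameter is derived, so a reader cannot see how much of each curve is missing or whether the half-life changed.

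**Working it through.** The plan's ratio is A/B; B/A is used below so that a rise reads as a rise. The limits are the same either way (1/1.25 = 0.80).

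**1. Reproduce the reported figures** (Table 11; n = 28, 26 df, t = 1.7056).
- AUC0-96, CV 18.56%: s² = ln(1 + 0.1856²) = 0.03387; SE = √(2 × 0.03387/28) = 0.04918; CI = 84.224% × exp(±1.7056 × 0.04918) = 77.45-91.59%; power = T26(ln 1.25/SE − 1.7056) = 99.56%. All match.
- Cmax, CV 40.07%: SE = 0.10313; CI 54.18-77.02%; power 67.46% (reported 67.47%).
- At this AUC variability the AUC criterion passes only if the observed B/A is at most 1.25 × exp(−1.7056 × 0.04918) = 1.149.

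**2. Share of the Treatment A curve beyond 96 h, one compartment:** 2^(−96/36) = 15.7%; 2^(−96/48) = 25.0%.

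**3. Clearance falls so that AUC0-inf rises by a factor R, volume constant.** Half-life h becomes R × h, and

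AUC0-96 ratio = R × (1 − 2^(−96/(R h))) / (1 − 2^(−96/h)).

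For R = 1.25:
- h = 36 h: 1.25 × 0.772/0.8425 = 1.146
- h = 48 h: 1.25 × 0.670/0.750 = 1.117

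**4. Two-compartment sensitivity**, on the planned sampling times, with assumed values: central volume 40-80 L, inter-compartmental clearance 30-60 L/h, clearance 10-14 L/h, absorption rate 2/h, peripheral volume solved to give a 36 or 48 h half-life. Between 78% and 89% of the curve is covered. A true 25% rise shows as 14-18%, and Cmax moves only 1-3%.

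**5. Chance of passing when the true rise is 25%** (two one-sided tests, n = 28, reported CVs):

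| Endpoint and model | Apparent rise | Passes AUC criterion |
|---|---|---|
| AUC0-inf | 25% | 5% |
| AUC0-96, one-compartment, 36 h | 14.6% | 53% |
| AUC0-96, one-compartment, 48 h | 11.7% | 72% |
| AUC0-96, two-compartment | 14-18% | about 58-30% |

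Cmax must also pass. At CV 40.07% it does so 35.2% of the time if its true ratio is 1.02 and 35.8% if 1.00. Assuming independence, both criteria pass between 0.533 × 0.352 = 19% and 0.721 × 0.358 = 26% of the time (one-compartment), against 0.05 × 0.352 = 2% with AUC0-inf.

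**6. Other mechanisms.**
- Absorption only: the half-life is unchanged, so the truncated share cancels and there is no bias.
- Clearance and volume cut equally: the half-life is unchanged, so no bias.
- Volume only, 20% cut: the true AUC0-inf ratio is 1.00. One-compartment AUC0-96 gives 0.9008/0.8425 = 1.07 (36 h) or 0.8232/0.750 = 1.10 (48 h). A two-compartment model (central volume 50 L, inter-compartmental clearance 40 L/h, clearance 13 L/h) gives 1.05 or 1.07. Here AUC0-96 overstates.

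**7. The observed result.** B/A = 15996.644/13473.043 = 1.187. Solving for the AUC0-inf rise that produces it:

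| If the effect is on | Rise in AUC0-inf |
|---|---|
| Absorption | 19% |
| Clearance, two-compartment (parameters of step 6) | 27% (36 h), 31% (48 h) |
| Clearance, one-compartment | 33% (36 h), 44% (48 h) |

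**The case against.** Much of the case on the other side stands.

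- **The rule tests whole intervals for two parameters.** A reader might infer that any AUC0-96 ratio below 1.25 would be called no interaction. It would not: the observed ratio must be at most about 1.149, and Cmax must pass as well. The joint figure of 19-26% is the relevant one for the overall conclusion.
- **The completed study declared an interaction.** Both intervals fell outside the limits, so no conclusion is reversed.
- **One compartment fits poorly.** Section 2.2.3 describes a 6- to 8-hour distribution phase. From the Treatment A Cmax of 1456, one compartment would imply AUC0-96 = 1456.085 × h/ln 2 × coverage, about 64,000 (36 h) to 76,000 (48 h), against 13,473 reported on the same unit scale. The 33-44% reading is therefore an upper bound.
- **Clearance is only one named route.** The protocol says clearance and/or volume. The observed Cmax rise (2254.118/1456.085 = 1.55) is far more than clearance alone would give, so absorption or volume probably contributes.
- **Urine helps.** A reader might infer that without half-life the trial cannot separate clearance from absorption. It partly can. Amount in urine barely changed (123523.87/122606.02 = 1.007), so Ae0-96/AUC0-96 fell by about 15% (1.007/1.187 = 0.849). That rests on geometric means, has no interval and assumes complete collection, but it points to a renal clearance component. The CLR formula as planned, over 0-240 h, cannot be computed from 96 h of samples.
- **The Section 2 remark is background.** It says "The sampling times for single-dose studies should be planned so that the mean difference between the" Cmax and AUC0-72 is below 20 percent. Those quantities have different units, but neither Section 9 nor the SAP applies the remark as a check, so nothing depends on it.

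What survives is the directional bias under a clearance effect and the absence of any reported quantity that would show it.

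**Conclusion.** The concern holds as a conditional one about effect size. If spironolactone lowers digoxin clearance at constant volume, AUC0-96 turns a true 25% rise into about 12-15% (one-compartment) or 14-18% (two-compartment). That raises the chance of meeting the AUC criterion alone from 5% to 53-72% or 30-58%, and of meeting both criteria from about 2% to 19-26% (one-compartment).

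For the completed study, the observed 1.187 is compatible with an AUC0-inf rise of about 19% if absorption drives it and roughly 27-31% if clearance does. The reported parameters do not settle which. A reader might infer that the true rise was 33-44% or that the interaction conclusion is unsafe. The documents support neither.

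Assumptions: the protocol's half-life range; compartmental models with assumed parameters; the reported CVs; independence of the Cmax and AUC decisions for the joint figure.

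**What to change.** In Protocol Section 9 and the SAP, add for each subject and period: terminal slope, half-life, AUC0-inf and percent of AUC extrapolated, from the existing 24, 36, 48, 60, 72 and 96 h samples. State the minimum number of points for the slope, and exclude concentrations set to zero for being below the quantification limit from it. Report the AUC0-inf geometric mean ratio and 90% CI beside AUC0-96 as a supportive analysis, and flag subjects whose extrapolated share exceeds a stated threshold.

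Do not make AUC0-inf an additional pass/fail gate. In the one-compartment 48 h case about 25% of the Treatment A curve and 33% of the Treatment B curve (R = 1.25) would be extrapolated, which exchanges truncation bias for extrapolation error.

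For the completed study, re-run the non-compartmental analysis, add the rows to Tables 10 and 11, and label them post hoc. The cost is one further run on existing concentrations and a few table rows. The downside is that some subjects may have a large extrapolated part, which the new column will show.
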